Investigator Studies Program (MISP) Protocol and Procedures	
	Section #1 - MISP Protocol Identification
Study Title:	The title of the protocol should include study design, indication and, where applicable, dosage, dosage form, and comparative agent(s). Single oral dose of azithromycin1 gm with or without amoxicillin2 gm to prevent peripartum infection and sepsis in laboring high-risk women: 3-Arm RCT
Request Date:	11/20/2015; Updated 6/13/2017; 10.1.2017; 11.28.17; 10/20/2018
Institution Name	University of Alabama at Birmingham/Cameroon Health Initiative
Investigator Contact Information: – Full address – Phone No. – Fax No. – e-mail address	[name], MD, PhD Professor, Department of Obstetrics and Gynecology Director, Center for Women's Reproductive Health & Maternal-Fetal Medicine Division [name] [contact] [contact] Email: [contact]

Castion #2. Care Brotocal		
	Section #2- Core Protocol	
2.1 Objectives & Hypotheses	Primary Objective : To test the effectiveness of a single adjunctive oral dose of a) 1g of azithromycin and b) 1g of azithromycin + 2g of amoxicillin, each compared to c) usual care alone (placebo group)in reducing maternal peripartum infections and sepsis in at-risk laboring women in a LIC setting. Hypothesis #1 : A single, oral dose of a) 1g azithromycin or b) 1g azithromycin+2g amoxicillin given for prolonged labor or prolonged membrane rupture in term pregnant women will reduce the risk of peripartum infections and sepsis.	
	Secondary Objectives: 1. To collect and story specimens to estimate the prevalence of mycoplasma and ureaplasma in the genital tract, placenta and chorioamnion and assess whether their presence is associated with peripartum infection in LICs.	
	Hypothesis #2: The presence of genitalureaplasma and mycoplasmas in the placenta and chorioamnion of laboring women will be strongly associated with maternal peripartum infections (similar to our findings in the US).	
2.2 Background & Rationale, Significance of Selected Topic & Preliminary Data	Maternal bacterial infection and sepsis during pregnancy and the puerperium accounts for approximately 10% of the global burden of maternal deaths. This places it among the top 5 causes. ¹ The appropriate use of antibiotic prophylaxis for cesarean delivery and antiseptic agents are among the most effective preventive interventions as highlighted by the recent WHO guidelines for maternal peripartum infections (access guidelines at: http://www.who.int/reproductivehealth/publications/maternal perinatal health /peripartum-infections-guidelines/en/). ¹ Cesarean delivery is the strongest risk factor for maternal peripartum infection including endometritis, wound infection and sepsis (increasing risk by at least 5 to 10 times compared to vaginal delivery). ² Antibiotic prophylaxis, preferably prior to incision, in particular, among several strategies, effectively reduces the risk of infection and associated high health care and personal costs. ^{1,3-5} In a recently completed multicenter US randomized clinical trial (abstract attached), we have demonstrated a further 50% reduction in the risk of maternal peripartum infection by adding a single 500mg intravenous dose of azithromycin to the standard prophylactic regimen (a single intravenous dose of azithromycin to the standard prophylactic regimen (a single intravenous dose of refazolin 1-2g or ampicillin) in the highest-risk group of women who undergo cesarean delivery following labor or membrane rupture for at least 4 hours(see trial registration at: https://clinicaltrials.gov/ct2/show/NCT01235546?term=[name]&rank=2). This work builds on, and is supported by, over 20 years of research on maternal infections including genital mycoplasmas and ureaplasmas (when specific methods are utilized to identify them). In sum, the use of a single dose of cefazolin or ampicillin for cesarean delivery is associated with a 50% reduction in risk of infection/sepsis. Adding azithromycin to this standard regimen further reduces post-cesarean infection risk by 50%. It is unknown whethe	

2

and sepsis attributable to cesarean delivery is minimal because of the low cesarean delivery rate of 5-10% or lower (compared with 20-30% or higher in the US and many high income countries).¹⁸ Therefore, strategies that address maternal peripartum infection and sepsis in the developing world should focus on identifying and preventing (or treating) infection in high-risk women who have a vaginal birth (or abortion). There is an increased risk of infection in women who undergo prolonged labor ≥18-24 hours (at least 2 fold) or membrane rupture ≥8-12 hours (2-3 fold in our study) compared to women who do not experience these risk factors. These risk factors identify a large group of women who are at the highest risk for maternal peripartum infections (chorioamnionitis and endometritis) and sepsis after a vaginal delivery. Indeed, the recent WHO Guidelines articulated the following among research priorities: what are the benefits of initiating prophylactic antibiotics after prolonged rupture of membranes?¹Furthermore, a recent JHPIEGO consultative meeting on enhancing the focus on maternal infections suggested that "Attention to identification and prompt management of prolonged labor and prolonged rupture of membranes is critical to reduce disease and death due to maternal sepsis".

Therefore, drawing from our findings with the azithromycin-based extended antibiotic prophylaxis strategy for cesarean delivery in the US, we propose to adapt the intervention and evaluate the role of a single oral dose of azithromycin (with or without oral amoxicillin) to prevent maternal peripartum infection and sepsis in women planning a vaginal delivery who have prolonged labor (\geq 18 hours) or prolonged membrane rupture (\geq 8 hours). The current global standard of care (including at the proposed study sites) is that antibiotics are not given solely for these risk factors.

Azithromycin is available as a generic agent. It has a bimodal half-life of up to 70 hours in the non-pregnant population; although it is not as well studied in the pregnant population. Azithromycin covers a broad spectrum of bacteria (including gram-positive cocci, genital ureaplasmas and mycoplasmas and certain gram-negative bacilli and anaerobes) that are associated with maternal infections, which are often polymicrobial (chorioamnionitis, endometritis and perineal wound infection) and sepsis. Amoxicillin mirrors the standard penicillin or cephalosporin recommended for prophylactic use for cesarean delivery and is also commonly available in LICs as a generic agent.¹The use of single prophylactic doses minimizes the likelihood of antimicrobial resistance (although this will need to be monitored). Azithromycin is currently recommended to treat or prevent several infections in pregnancy including gonorrhea (1g po), chlamydia (1 g po) and mycobacterium avium complex prophylaxis (600mg twice/week or 1.2 g weekly po). It is sometimes used for perioperative prophylaxis in patients at risk for endocarditis (500mg po). Considering our success with 500mg IV for cesarean prophylaxis, the 40% bioavailability of oral azithromycin and the approved doses for treatment of infections, we will use 1g po of azithromycin for the proposed intervention. Similarly, amoxicillin has a bioavailability of 80-90% and is used to treat several infections at doses of 500mg-2g po. Considering that ampicillin is used at a dose of 1-2g for cesarean prophylaxis, a 2g optimal dose of amoxicillin will be used for the study intervention.

The best approach to this evaluation in order to influence future uptake into clinical practice is a randomized trial of these simple regimens vs. the usual standard of care (including antibiotic prophylaxis after 18 hours of

[figure not shown]
MISP Protocol and Procedures

[figure not shown]
3

	membrane rupture). The key primary outcomes will include any maternal bacterial infection (sepsis, chorioamnionitis, endometritis, or other wound infection) and/or maternal death prior to discharge from the hospital. The primary endpoint is the incidence of maternal peripartum infections that lead to sepsis and death. For this study we will assume an effect size of 50% which mirrors the minimum effect size observed with standard antibiotic prophylaxis for cesarean delivery. The baseline risk of infection with prolonged membrane rupture or labor is not well defined and ranges from 15-30%. We assume a baseline risk of 20% for the composite and this test of concept will also help better quantify baseline risks.
2.3 Study Design	Study design:3-arm randomized controlled trial. The investigational regimens are 1g of azithromycin and 1g azithromycin+2g amoxicillin; the common control arm is usual care at sites + placebo. We will design placebo for each, amoxicillin and azithromycin, with the assistance of the CBCHS Central Pharmacy, using identical capsules containing each antibiotic or matching placebo (non-antimicrobial agent e.g. starch) to accomplish blinding: 1 g azithromycin/placebo for amoxicillin, 1 g azithromycin/2 g amoxicillin vs. placebo for azithromycin /placebo for amoxicillin. Study location:4-6 hospitals with approximately 8,000 deliveries in total per year in Cameroon. These hospitals belong to (or are affiliated with) the CBCHS, a well-established major local partner of our UAB Cameroon Health Initiative (CHI UAB). CHI UAB is collaboration between a multidisciplinary group at UAB (multiple schools and departments) and major health organizations in Cameroon including the CBCHS, major medical schools and the Ministry of Health to improve health care through research, education and service delivery. CHI UAB has a dedicated in-country program coordinator based at the CBCHS with a background in laboratory sciences (MSc) and public health (MPH). The CBCHS is a very well organized system with 7 major hospitals and over 80 health care units providing maternity care in 6 of the 10 regions of Cameroon. We will start at BBH, MBH, BHM and Mboppi and add a 5th site later if necessary.
	Inclusion criteria: Pregnant women with singleton pregnancy in labor at term ≥37 weeks who plan to deliver vaginally and have a) prolonged membrane rupture (≥ 8 hours) or prolonged labor (≥18 hours)* The study is restricted to those at term because those who are preterm may be more likely to receive antibiotics for other reasons and per recommendations. Exclusion criteria: Evidence of chorioamnionitis or other infection requiring antibiotics at time of eligibility, allergy to azithromycin or amoxicillin or any ingredients in the placebo, or plan for cesarean delivery prior to enrollment. Interventions: 1g po Azithromycin/ placebo for amoxicillin, 1g po Azithromycin. Subjects will be stratified by enrollment site.
	develop maternal peripartum infection or death prior to discharge from the hospitalup to 6 weeks postpartum defined as one or more of: a) Chorioamnionitis: Fever (>100.4°F/38°C on two occasions 30 minutes apart or ≥102°F/39°C on one occasion) in addition to one or more of the following: fetal tachycardia >160bpm, maternal tachycardia>100bpm, uterine tenderness or purulent lochia prior to delivery, or diagnosis by a clinician.

1

4

Trained research staff in maternity outcomes reporting at each center (also blinded to study medications) will be responsible for all screening and research data abstraction from patient medical records with the help of clinical investigators and staff. Each hospital will have a designated investigator physician. Research nurses will undergo centralized specific training to screen and ascertain study outcomes. Screening will occur on labor and delivery in the selected CBCHS units and will be conducted by dedicated trained study staff with the assistance of clinical staff. The screening form will be used and completed for each patient screened. Potential subjects will be approached by trained research staff for written consent in English or French. Patients who cannot read will have the consent form read to them. Those that indicate they do not understand will be excluded. Study subjects will be randomized only after eligibility criteria have been confirmed and the patient has consented to participate by signing the informed consent form. The randomization form will be used to complete randomization

2. Randomization and Drug allocation concealment: Enrolled subjects will be randomly assigned in a 1:1:1 ratio to one of the two prophylactic oral regimens or to no treatment/placebo using either a web-based randomization sequence with varying block sizes and stratified by study site. Alternatively, considering challenges to internet access, a computer-generated randomization scheme with appropriate sequence of use of the interventions will be confidentially maintained in the pharmacy at each site and used to accomplish the random allocation of consecutive patients.

Blinding: As previously discussed we will plan to accomplish blinding with placebo by working with the CBCHS central pharmacy to accomplish identical capsules with and without the active medications. These medications will be packaged according to the predefined sequence into opaque envelopes containing the designated medication. All packages will have capsules that represent azithromycin or placebo and amoxicillin or placebo. The envelopes will be stored in sequential order until a patient is ready for randomization,

3. Medication distribution: The allocated therapy will be provided by the pharmacy staff. Clinical supplies will be received by a designated person at the study site, handled and stored safely and properly, and kept in a secured location for use in study participants as above. Clinical supplies will be dispensed in accordance with the protocol. The pharmacy is responsible for keeping accurate records of the clinical supplies, the amount dispensed for use by the patients, and the disposition at the end of the study.

The allocated therapy will be provided by the pharmacy staff to study staff for distribution.

The patient is considered randomized once the medication is dispensed from the pharmacy and sequential number posted on the patient specific randomization form. The study medication will be initiated immediately (prior to delivery).

On labor anddelivery, achorioamnion swab will be collected by trained research staff into storage tubes with appropriate medium and stored in a dedicated study freezer. Maternal blood will also be collected into the tube provided and frozen as well. Specimens will be shipped to UAB and kept in a biorepository

MISP Protocol and Procedures

I

7

for future testing (shipped in batches as boxes get full). Of note all CBCHS facilities have back-up generators to ensure continuous power.

Data Collection: Research staff will use data collection forms to collect patient information including contact information, characteristics and clinical outcomes. In addition to outcomes at time of discharge, participants will be followed-up at 6 weeks in person at their postpartum visit or by phone. They will be asked about any post-delivery problems and admissions for them or their baby and records will be reviewed to validate the outcomes. Complete baseline and outcome data will be collected by trained study nurses by direct interview and chart review using the forms provided. Contact and other confidential information will be known only to the local staff at each site. No confidential information will be entered into the database.

Outcome adjudication: We will review and validate primary outcomes centrally in a blinded fashion -2 investigators will review de-identified records to confirm that the pre-defined criteria are met and agree on the diagnosis. Any initial disagreement will be resolved by consensus of the reviewers. If necessary a final adjudication will be made by the study PI.

Data Management: A study statistician and data manager located at UAB will be responsible for coordinating overall data management for the trial. A designated in-country site PI will be responsible for day-today supervision of data management, with everyone using the same standardized data collection tools. Data management at each site includes procedures for data entry, data editing, and compilation; data transmittal and quality control, data verification, confidentiality and security. Data will be collected and managed with Research Electronic Data Capture (REDCap), an established, secure web-based data capture and management tool developed at Vanderbilt University and supported by the Data team at UAB. We have been able to use REDCap for remote capture of data entered in Cameroon into the database at UAB in our ongoing survey of infection practices. Data quality will be assessed monthly by the data manager, and remedial measures, including re-abstraction of data and retraining of staff and edits will be used as needed to enhance data quality. Overview of study management: [name] will be PI and will coordinate with and local project director, [name] to provide local study oversight in collaboration with other team members of CHI UAB and the [name]. [name] will be project coordinator. Physicians at each site will be designated as site PIs and the central pharmacy will be responsible for packaging medications. The CHI-UAB research assistant team will help with implementation at each site. The study will be discussed every 2 weeks at UAB during the CHI UAB Meeting with the [name]. [name] will correspond with [name] on a weekly basis and she will oversee the research assistants. [name] or a team member investigator from the US will visit Cameroon every 4-6 months and tour all sites to ensure the proper implementation. UAB has established a subcontract to CBCHS for management purposes.

6. Study Administration

This study will be conducted at 4-6 hospitals with approximately 8,000 deliveries in total per year in Cameroon. These hospitals belong to (or are affiliated with) the CBCHS, a well-established major local partner of our UAB Cameroon Health Initiative (CHI UAB). CHI UAB is collaboration between a multidisciplinary group at UAB (multiple schools

MISP Protocol and Procedures

8

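### Does the plan's disagreement with itself over usual-care antibiotics at 18 hours of membrane rupture undermine the control arm or the sample size?

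*Combined protocol and SAP*

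**What the plan says.** Two statements in section 2.2 (Background & Rationale) bear on usual care.

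- After naming the entry risk factors (labor of at least 18 hours, membrane rupture of at least 8 hours), the plan says that, globally and at the proposed sites, "antibiotics are not given solely for these risk factors".
- The closing paragraph describes the comparator as "the usual standard of care (including antibiotic prophylaxis after 18 hours of" membrane rupture.

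Elsewhere the control arm is named without listing its contents. Section 2.1 has "usual care alone (placebo group", with the active regimens called adjunctive. Section 2.3 has "the common control arm is usual care at sites + placebo". The randomization paragraph refers to "one of the two prophylactic oral regimens or to no treatment/placebo".

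The inclusion criteria in section 2.3 are "prolonged membrane rupture (≥ 8 hours) or prolonged labor (≥18 hours", with no upper limit on rupture. The only exclusion that touches on antibiotics is infection requiring them.

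On the planning risk, section 2.2 says that baseline risk "is not well defined and ranges from 15-30" percent, and then "We assume a baseline risk of 20% for the composite". Section 2.7 uses 20%, a 50% reduction, 80% power and alpha 0.025 per comparison to reach 241 per group and 750 in total.

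**The concern.** Rupture of 18 hours or more lies inside rupture of 8 hours or more. For women in that overlap, one sentence says antibiotics are not given for rupture alone and the other says prophylaxis is part of usual care. These women can be enrolled. A woman enrolled at, say, 10 hours can also pass 18 hours before she delivers, so the overlap is not limited to those already at 18 hours when randomized.

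Two things would be at stake. First, a reader could not say what the study drugs were added to in this group. Second, the 20% might be a risk without antibiotics. If some control women then receive prophylaxis, the true control risk would be lower than planned, or the study drug might add less in women already treated. Either would reduce power, and the margin is small.

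**Working it through.** **1. Reproduce the plan's figure.** Inputs from section 2.7: control risk p1 = 0.20, active risk p2 = 0.10, power 80%, alpha 0.025 per comparison. Sidedness is not stated. Two-sided reproduces the figure, whereas one-sided would give 199.

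n per group = [z(1−α/2)·√(2·p̄·(1−p̄)) + z(1−β)·√(p1(1−p1) + p2(1−p2))]² / (p1 − p2)²

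With p̄ = 0.15, z(0.9875) = 2.2414 and z(0.80) = 0.8416:

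n = [2.2414 × √0.255 + 0.8416 × √0.25]² / 0.01 = [1.1319 + 0.4208]² / 0.01 = 241.1

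The plan's 241 is right to rounding. The planned total gives 750 / 3 = 250 per group, where power is Φ[(0.10 × √250 − 1.1319) / 0.5] = Φ(0.899) = 81.6%.

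**2. Power over the plan's own 15–30% range**, at 250 per group with the 50% reduction kept:

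| Control risk | Active risk | n per group for 80% | Power at 250 |
|---|---|---|---|
| 15% | 7.5% | 336 | 66.1% |
| 20% | 10% | 241 | 81.6% |
| 25% | 12.5% | 184 | 91.3% |
| 30% | 15% | 146 | 96.4% |

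Power reaches 80% from a control risk of about 19.4%, which is 0.6 percentage points below the planning value.

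**3. What the ambiguity could do.** The documents give neither the share of women who receive usual-care prophylaxis nor its effect. As an assumption only, let 20% be the risk without antibiotics, and let a share f of control women receive prophylaxis that halves their risk. The control risk is then 0.20 × (1 − 0.5f). Two cases are shown: the study drug still halves the resulting risk, or it adds nothing in women already treated (active risk then stays at 10%).

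| f | Control risk | Power, drug still halves risk | Power, no added effect in treated women |
|---|---|---|---|
| 10% | 19.0% | 78.9% | 73.3% |
| 25% | 17.5% | 74.6% | 57.7% |
| 50% | 15.0% | 66.1% | 29.0% |

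If 20% is already the risk under usual care and the 50% reduction holds, power stays at 81.6%.

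**4. Does the comparison itself depend on which sentence is right?** The contrast is blinded study product against matching placebo, each on top of site care, randomized 1:1:1 and stratified by site. Nothing in the available text of the design or procedures assigns or withholds usual-care antibiotics by arm. Whichever practice a site follows, it applies to all three arms. The chi-square test and relative risk in section 2.7 therefore estimate the effect of adding the drug to usual care, which is the adjunctive question in section 2.1.

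**The case for a change.** The strongest case for a change is that the comparator is ambiguous for an eligible group, that the power margin is only 0.6 percentage points of control risk, and that the remedy is cheap: reconcile the sentences, state the basis of the 20%, print power across 15–30%, and pre-specify rupture of 18 hours or more as a covariate in the planned logistic regression.

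Part of this stands. Read literally the sentences disagree, and they have to be reconciled. A general rule with an exception from 18 hours is a plausible reading, but the plan does not state it. The public text also shows signs of a marked-up file, such as a stray formatting note and run-together words in the outcome definition, so one sentence may be superseded. That cannot be shown either way.

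The rest does not lead to a better plan.

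- **The 20%.** It is introduced in the same paragraph as the description of usual care and is used as the control-arm risk, so risk under usual care is its natural reading. On that reading the stated power holds.
- **The power table.** It would be the same if the two sentences agreed. It reflects uncertainty in the baseline risk, which section 2.2 acknowledges and says the trial will help to quantify.
- **Attenuation.** The no-added-effect column above is severe, but nothing in the documents supports it. Their only add-on evidence, from cesarean delivery, is a further 50% reduction when azithromycin joined standard prophylaxis. That setting differs, so it does not settle the matter, but it points the other way.
- **The covariate.** Rupture duration at randomization misses women who pass 18 hours later. As a main effect in a secondary model it cannot show whether the drug adds less in treated women, and it leaves the primary test as it is.
- **Labels.** Calling control no treatment in the randomization paragraph can be read as describing the allocated product. Calling the placebo-arm colonization result in section 2.7 a baseline is likewise a matter of description: if usual-care antibiotics came before the swab, it is the prevalence under usual care.

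**Conclusion.** The inconsistency is real but is one of wording. The two statements in section 2.2 must be reconciled into one description of the usual care common to all arms. Which practice is right is not judged here. Nothing in the design, sample size, randomization or primary analysis needs to change.

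The randomized comparison is unbiased under either description, because usual care is not assigned by arm. The sample size is correct for its stated inputs: 241 per group for 20% versus 10%, with 81.6% power at 250. This rests on a two-sided alpha of 0.025 per comparison, on 20% being the risk under usual care, and on the 50% reduction holding. If the control risk is lower, power falls, to 66.1% at 15%, but that exposure is the baseline-risk uncertainty the plan already states. Its link to antibiotics at 18 hours cannot be quantified from the documents, and choosing between the two sentences would not supply the missing share of treated women.

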	4.5. Follow-up
	• Through discharge and then up to 6 weeks as previously described.
	4.5.1 Withdrawals: Patients who withdraw from the study after randomization will be excluded from further follow-up. Outcomes ascertained up until the time of withdrawal will be reported in intent to treat fashion. Those who withdraw prior to the 6-week window for ascertaining the primary outcome will be accounted for by randomizing an equal number of additional patients.
2.6 Study Duration	3 years
2.7 Statistical Analysis and Sample Size Justification Data Management	Data management: A study statistician and data manager located at UAB will be responsible for coordinating overall data management for the trial. A designated in- country site project director and staff will be responsible for day-today supervision of data management, with everyone using the same standardized data collection tools. Data management at each site includes procedures for data entry, data editing, and compilation; data transmittal and quality control, data verification, confidentiality and security. Data will be collected and managed with Research Electronic Data Capture (REDCap), an established, secure web-based data capture and management tool developed at Vanderbilt University and supported by the Data team at UAB. We have been able to use REDCap for remote capture of data entered in Cameroon into the database at UAB in our ongoing survey of infection practices. Data quality will be assessed monthly by the data manager, and remedial measures, including re-abstraction of data and retraining of staff and edits will be used as needed to enhance data quality.

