	Analyses: Data analyses will follow the CONSORT guidelines. Analyses will be by intention-to-treat in which subjects will be analyzed in the group to which they were randomized, regardless of whether or not they received the assigned intervention. Analyses will be performed at the Center for Women's Reproductive Health, University of Alabama at Birmingham. The key analyses for this study are the comparisons reflected by the primary and secondary aims. The primary analysis will compare the incidence of the composite peripartum infection outcome between each of the active groups and the control groups – a chi-square p-value as well as the relative risk and 95% CI will be computed for each comparisons. The secondary outcomes will be similarly compared. Student's t-test comparisons of continuous outcomes will be done. Standard comparisons of covariate characteristics at baseline between groups will be done. It is anticipated that the randomization scheme will balance the groups for these covariates; however, secondary analyses of relevant outcomes using logistic regression adjustments will be implemented to account for any suggested confounding. A secondary comparison will examine the 2 active groups relative to each other. The data from the ureaplasma/mycoplaema_testing_will_be_similarly_compared_with_the
	 Compared with the baseline colonization rate will be reflected by the findings in the no-treatment/placebe group. Sample Size Calculation, Primary Outcome: This has been previously presented above and is shown here as a reminder. Sample size: Up to15-30% of women who have prolonged labor or membrane rupture will have one or more infections included in the primary endpoint. We assume a baseline risk of 20%. To demonstrate a 50% reduction in peripartum infections in the high-risk group of laboring women (of the same order observed in high risk group who have cesarean) with antibiotic prophylaxis with 80% power and alpha of 0.025 per primary comparison (0.05 total), 241 women per group are needed. Thus 750 women will be needed for the 3 arm

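### Section 2.2 ends the primary outcome at hospital discharge and then narrows it to infections leading to sepsis and death, while 4.5.1 ascertains it over 6 weeks

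*Combined protocol and SAP*

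**What the plan says.** The endpoint is described in several places.

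- **2.2 Background & Rationale, endpoint paragraph.** The key primary outcomes are to include "any maternal bacterial infection (sepsis, chorioamnionitis, endometritis, or other wound infection) and/or maternal death prior to discharge from the hospital". The following sentence reads: "The primary endpoint is the incidence of maternal peripartum infections that lead to sepsis and death". The same paragraph sets the 20% baseline risk for the composite.
- **2.3 Study Design, outcome definition.** A discharge limit runs straight into a limit of 6 weeks postpartum, with no space or conjunction between them. The list of components follows; only chorioamnionitis is visible in the text available.
- **Data Collection.** Beyond outcomes at discharge, "participants will be followed-up at 6 weeks in person at their postpartum visit or by phone", and "records will be reviewed to validate the outcomes". It does not say which time point defines the primary outcome.
- **4.5 Follow-up.** "Through discharge and then up to 6 weeks as previously described".
- **4.5.1 Withdrawals.** "Those who withdraw prior to the 6-week window for ascertaining the primary outcome" are replaced by randomizing the same number of additional women.
- **2.7 Statistical Analysis.** "The primary analysis will compare the incidence of the composite peripartum infection outcome between each of the active groups" and control, by chi-square test and relative risk with 95% CI. No window is given. The 15-30% range is the proportion of women who "will have one or more infections included in the primary endpoint"; the 20% assumption is the next sentence, also without a window.

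**The concern.** A binary primary outcome needs one event set and one closing date. Here 2.2 and 4.5.1 give different closing dates, and the two adjacent sentences in 2.2 give different event sets.

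Endometritis and wound infection can first appear after a woman goes home. Whether those cases count depends on which statement is followed. The two adjudicators must confirm pre-defined criteria, and the time limit belongs to those criteria. The same choice decides what enters both primary comparisons. If it is left unsettled, the window could be fixed after outcome data have been seen.

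**Working it through.** **Step 1. Classify the same event under each statement.**

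| Event | 2.2, discharge limit covers infection and death | 2.2, discharge limit covers death only | 4.5.1 |
|---|---|---|---|
| Infection before discharge | counts | counts | counts |
| Infection first appearing after discharge, within 6 weeks | does not count | no limit stated | counts |
| Maternal death after discharge, within 6 weeks | does not count | does not count | counts |

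Neither reading of 2.2 agrees with 4.5.1. The narrower grammatical reading leaves infection without a window and still conflicts on death.

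**Step 2. Compare the two sentences in 2.2.** An infection before discharge that resolves without sepsis or death counts under the first sentence. Read literally, the second sentence excludes it. The 2.3 definition, which needs only one or more listed conditions, agrees with the first.

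**Step 3. Reproduce the sample size.** Inputs from 2.7: 20% v 10%, alpha 0.025 per comparison (sidedness not stated; two-sided reproduces the figure), 80% power. Pooled-variance formula without continuity correction:

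n = [z(1-α/2)·√(2·p̄·(1-p̄)) + z(0.80)·√(p1(1-p1) + p2(1-p2))]² / (p1-p2)²

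with p̄ = 0.15, z(0.9875) = 2.2414 and z(0.80) = 0.8416:

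- 2.2414 × √0.255 = 1.1319
- 0.8416 × √0.25 = 0.4208
- n = (1.1319 + 0.4208)² / 0.01 = 241.08, against 241 in the plan

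Power is 0.7999 at 241, 0.8017 at 242 and 0.8156 at 250 per arm (750/3). The plan's figure stands.

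**Step 4. Size the ambiguity under stated assumptions.** Expected events at 250 per arm: 0.20 × 250 = 50 control and 0.10 × 250 = 25 active. Take 20% v 10% as the 6-week rates, and assume the same share s of events first appears after discharge in both arms. The values of s are assumptions, not document figures.

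| s | Control events changing status | Active-arm events changing status | Rates to discharge | Power at 250 |
|---|---|---|---|---|
| 10% | 5 | 2.5 | 18% v 9% | 0.761 |
| 25% | 12.5 | 6.25 | 15% v 7.5% | 0.661 |

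With equal shares the relative risk stays at 0.50 and only its precision changes. With unequal shares the relative risk would move too. The power column is illustrative only: 18% and 15% both lie within the protocol's own 15-30% baseline range.

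**The case against.** The strongest reply is that 6 weeks is plainly intended and 2.2 is only loosely worded rationale. Much of that stands. The joined phrase in the 2.3 definition looks like tracked-change residue in which 6 weeks replaced discharge, so it supports 4.5.1. The Data Collection text already plans 6-week ascertainment. The second sentence in 2.2 can also be read as explaining why these infections matter. But 2.2 says in terms what the primary endpoint is and sets the planning rate for it. If the definition was updated to 6 weeks, 2.2 was not.

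A second reply is that the missing text might settle the matter. The components after chorioamnionitis, and the text just before the newborn-outcome bullets, were not available. A clear statement there would show which window governs, but 2.2 and 4.5.1 would still disagree.

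Three stronger readings are tempting and not supported:

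- A reader might count the 2.3 definition as a further contradiction. Its joined wording is more likely an editing remnant that favours 6 weeks.
- A reader might count the silence of 2.7 as a contradiction. An analysis section may rely on a definition given elsewhere; naming the window there is useful, but its absence is not a conflict.
- A reader might infer that the trial is underpowered. The documents give no event rate by window, and the sample size reproduces.

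**Conclusion.** The point holds as an inconsistency of wording in the primary endpoint, and it should be corrected. The conflict between 2.2 and 4.5.1 does not depend on how 2.3 is read. Six weeks is the better supported window, on 2.3, Data Collection and 4.5.1 together, but that has to be inferred.

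The size in this trial is unknown because the share of post-discharge events is not in the text available. The assumed 10% and 25% show only that the number of reclassified events need not be trivial. The conclusion rests on the text that could be read and does not rest on power.

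**What to change.** These changes make the plan say one thing:

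- In 2.2, replace the discharge limit with a limit of 6 weeks postpartum, and delete the qualifier that ties the endpoint to progression to sepsis and death.
- In the 2.3 definition, clear any discharge wording that remains beside the 6-week limit.
- In the 2.7 primary-analysis sentence, refer to the 6-week composite.
- State once that the 20% planning rate refers to that 6-week window.

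The cost is wording only, since 6-week contact and record review are already planned. The downside is that some 6-week outcomes will be missing among women not reached in person or by phone, so report the number missing in each arm. Women who withdraw before the 6-week window are already replaced under 4.5.1, so they should not be set against the small margin of 250 planned over 242 needed for at least 80% power (8 per arm).
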